8.8. Analysis of Other Efficacy Endpoints

8.8.1. eGFR Endpoints

8.8.1.1. eGFR Chronic Slope over 1 Year

The slope of eGFR over approximately 1 year of randomized treatment evaluated following the initial acute effect of randomized treatment (ie, from Week 6 to Week 60; chronic slope over 1 year) will be analyzed via the mixed model random coefficients analysis described in [Section 8.5.1.1](#) using IAS at the time of interim analysis and FAS at final analysis. The response variable is the eGFR measured at on-treatment, post-baseline assessments during the randomized treatment period up to and including Week 60 for each patient.

8.8.1.2. eGFR Total Slope over 1 Year

The slope of eGFR over approximately 1 year of randomized treatment evaluated following initiation of randomized treatment (ie, from Day 1 to Week 60; total slope over 1 year) will be analyzed via the mixed model random coefficients analysis described in [Section 8.5.1.2](#) using IAS at the time of interim analysis and FAS at final analysis. The response variable is the eGFR measured at on-treatment, post-baseline assessments during the randomized treatment period up to and including Week 60 for each patient.

8.8.1.3. eGFR Absolute Change from Baseline

For the analysis of eGFR absolute change from baseline by visit (Week 2 to Week 112), an MMRM approach analogous to the model described in [Section 8.7.1](#) for percent change from Week 6 will be used, except that the response variable and corresponding baseline value is in original scale rather than natural log scale. Analysis will be performed using IAS at interim analysis and FAS at final analysis. At the interim analysis, only eGFR results through Week 60 will be included. Change from baseline will be derived at each visit by subtracting the coefficient for baseline used to derive the LS mean from the LS mean estimate for the visit. The LS mean estimate for $\beta_{\text{week } j * \text{treatment}}$ (ie, the treatment effect at the visit j of interest) from the MMRM model will be used to perform treatment group comparisons by visit.

8.8.1.4. eGFR Percent Change from Baseline

For the analysis of eGFR percent change from baseline by visit, an MMRM approach analogous to the model described in [Section 8.7.1](#) will be used. Analysis will be performed using IAS at interim analysis and FAS at final analysis. At the interim analysis, only eGFR results through Week 60 will be included. Change from baseline will be derived at each visit by subtracting the coefficient for baseline used to derive the LS mean from the LS mean estimate for the visit. The LS mean estimate for $\beta_{\text{week } j * \text{treatment}}$ (ie, the treatment effect at the visit j of interest) from the MMRM model will be used to perform treatment group comparisons by visit. Estimates and CIs will be converted to percentages via the following transformations:

$$[\exp(\text{least squares mean change from baseline in natural log(eGFR)}) - 1] \times 100$$

8.8.1.5. eGFR Percent Change from Week 6

For the analysis of eGFR percent change from Week 6 by visit, the estimates from the MMRM model used in the analysis of eGFR relative percent change from baseline by visit described in [Section 8.7.1](#) will be utilized. Analysis will be performed using IAS at interim analysis and FAS at final analysis. At the interim analysis, only eGFR results through Week 60 will be included. Statistical significance of the treatment effect at each visit after Week 6 will be assessed by comparing with the treatment effect at Week 6. Treatment effect refers to the treatment difference of sparsentan minus irbesartan. The LS mean estimate from the MMRM model will be used to perform treatment group comparisons. Estimates and CIs will be converted to percentages via the following transformations:

$$[\exp(\text{least squares mean change from Week 6 in natural log(eGFR)} - 1) \times 100$$

8.8.2. UP/C Endpoints

8.8.2.1. Proportion of Patients Achieving FPPE

For the analysis of the proportion of patients achieving FPPE, defined as UP/C ≤ 1.5 g/g (170 mg/mmol) and a $>40\%$ reduction from baseline, the by-visit estimates from the model described in [Section 8.6.1](#) will be utilized. Analysis will be performed using IAS at interim analysis and FAS at final analysis. At interim analysis, only FPPE results through Week 60 will be included. LS means for the probability of achieving FPPE (risk) for each treatment group and treatment effect (risk difference) at each visit will be extracted from the model. Relative risk ratio and odds ratio will also be presented.

8.8.2.2. UP/C Percent Change from Baseline

For the analysis of UP/C percent change from baseline by visit, an MMRM approach analogous to the model described in [Section 8.8.1.4](#) for eGFR percent change from baseline will be used for IAS at interim analysis and FAS at final analysis. At interim analysis, only UP/C results through Week 60 will be included. Change from baseline will be derived at each visit by subtracting the coefficient for baseline used to derive the LS mean from the LS mean estimate for the visit. The LS mean estimate for $\beta_{\text{week } j * \text{treatment}}$ (ie, the treatment effect at the visit j of interest) from the MMRM model will be used to perform treatment group comparisons by visit. Estimates and CIs will be converted to percentages via the following transformations:

$$[\exp(\text{least squares mean change from baseline in natural log(UP/C)} - 1) \times 100$$

8.8.2.3. Time to Achieve FPPE

The time to achieve FPPE (ie, time to first occurrence of FPPE), defined as UP/C ≤ 1.5 g/g (170 mg/mmol) and a $>40\%$ reduction from baseline, will be analyzed for IAS at interim analysis and FAS at final analysis using a Cox proportional hazards model with treatment and baseline UP/C (natural log) as fixed effects and stratified by randomization stratification variables. Patients who discontinue randomized treatment prior to achieving FPPE will be censored at the time of randomized treatment discontinuation. Patients who never met FPPE will be censored at the time of analysis (ie, data cut-off date for interim analysis or time of study discontinuation for final analysis) or the time of treatment completion in the randomized treatment period (whichever is earlier).

8.8.3. Other Quantitative Urinalysis Parameters

For the analysis of change from baseline by visit for other quantitative urinalysis parameters, a MMRM approach analogous to the model described in Section 8.8.1.4 for eGFR percent change from baseline will be used for IAS at interim analysis and FAS at final analysis. At interim analysis, only quantitative urinalysis results through Week 60 will be included. Change from baseline will be derived at each visit by subtracting the coefficient for baseline used to derive the LS mean from the LS mean estimate for the visit. The LS mean estimate for $\beta_{\text{week } j * \text{treatment}}$ (ie, the treatment effect at the visit j of interest) from the MMRM model will be used to perform treatment group comparisons by visit. Estimates and CIs will be converted to percentages via the following transformations:

$$[\exp(\text{least squares mean change from baseline in natural log(UP/C)}) - 1] \times 100$$

8.8.4. Other Responder Endpoints

The following responder endpoints will be summarized descriptively for FAS at both the interim and final analysis and compared (at final analysis only) between treatment groups using a CMH test controlling for the randomization variables:

- The proportion of patients reaching a confirmed 40% reduction in eGFR, ESRD, or death. ESRD is defined as initiation of RRT or sustained eGFR <15 mL/min/1.73² during the study (confirmed after repeat assessment of at least 14 days after initial assessment)
- The proportion of patients reaching a confirmed 30% reduction in eGFR, ESRD, or death
- The proportion of patients requiring initiation or intensification in immunosuppressive medication during the study
- The proportion of patients undergoing reduction in immunosuppressive medication during the study

Reduction of eGFR requires confirmation by a value at least 4 weeks after the initial value. If the last value on randomized treatment is the initial value for reduction or eGFR <15 mL/min/1.73² then the last value on randomized treatment is considered confirmed or sustained.

Initiation of RRT will be entered on the Concomitant Procedures eCRF as “chronic dialysis” or “kidney transplant” and on the Adverse Events eCRF as “progression of CKD leading to chronic dialysis” or “progression of CKD requiring kidney transplant”.

8.8.5. Other Continuous Endpoints

Changes from baseline to all post-baseline visits with respect to QOL scores (including KDQOL, PedsQL, EQ-5D-5L index value and VAS, EQ-5D-Y VAS) and blood pressure (including systolic and diastolic excluding Day 1 post-dose) values will be analyzed for FAS at final analysis using an MMRM model analogous to the one described in Section 8.8.1.4 for eGFR percent change from baseline will be used. Change from baseline for blood pressure will also be analyzed for IAS at interim analysis. Only blood pressure results through Week 60 will be included in the interim analysis.

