12.7.3. Additional Efficacy Analyses

For the analysis of eGFR absolute change from baseline by visit, a MMRM model will be fitted to the available eGFR data, incorporating all post-baseline visits at which eGFR was measured for each patient during the double-blind period. The model will include treatment, both stratification factors for randomization, baseline eGFR, visit (categorical), and visit-by-treatment interaction as fixed effects. In addition, patient will be included as a random effect.

The model will utilize REML estimation with Kenward-Roger method used to compute the denominator degrees of freedom for tests of fixed effects. An unstructured within-patient covariance structure will be assumed. If the model does not converge under the unstructured covariance matrix, the autoregressive-1 covariance structure will be used. The LS mean estimate for $\beta_{\text{WKj}*\text{treatment}}$ (ie, the treatment effect at the visit j of interest) from the MMRM model will be used to perform treatment group comparisons by visit.

For the analysis of eGFR percent change from baseline by visit, a MMRM approach analogous to the model described for the absolute change from baseline will be used, except that the

response variable will be natural log(eGFR) and corresponding baseline value natural log(baseline eGFR). The LS mean estimate for $\beta_{\text{WK}j^* \text{treatment}}$ (ie, the treatment effect at the visit j of interest) from the MMRM model will be used to perform treatment group comparisons by visit. Estimates and CIs will be converted to percentages via the following transformation:

$$[\exp(\text{LS mean change from baseline in natural log(eGFR)}) - 1] \times 100$$

For the analysis of eGFR percent change from Week 6 by visit, the estimates from the MMRM model used in the analysis of eGFR relative percent change from baseline by visit described above will be utilized. However, for this analysis, the statistical significance of the treatment difference at visit j (eg, Week 108 for the secondary endpoint) will be assessed by testing the following hypothesis:

$$H_0: (\beta_{\text{WK}j^* \text{treatment}} - \beta_{\text{WK}6^* \text{treatment}}) = 0, \text{ versus:}$$

$$H_1: (\beta_{\text{WK}j^* \text{treatment}} - \beta_{\text{WK}6^* \text{treatment}}) \neq 0,$$

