where $\beta_{\text{WK}j^* \text{treatment}}$ is the treatment effect at the visit j of interest and $\beta_{\text{WK}6^* \text{treatment}}$ is the effect estimate at Week 6. The LS mean estimate from the MMRM model will be used to perform treatment group comparisons by visit. Estimates and CIs will be converted to percentages via the following transformation:

$$[\exp(\text{least-squares mean change from Week 6 in natural log(eGFR)}) - 1] \times 100.$$

Change from baseline to all post-baseline visits during the double-blind period in natural log(UP/C) will be analyzed using a MMRM model analogous to the one described for percent change from baseline in eGFR. The LS mean estimate for $\beta_{\text{WK}j^* \text{treatment}}$ (ie, the treatment effect at the visit j of interest) from the MMRM model will be used to perform treatment group comparisons by visit. Estimates and CIs will be converted to percentages via the following transformation:

$$[\exp(\text{LS mean change from baseline in natural log(UP/C)}) - 1] \times 100.$$

The time to achieve the target reduction in UP/C during the double-blind period will be analyzed using a Cox proportional hazards model, stratified by randomized stratification variables, with a comparison between treatment groups. Patients who discontinue from treatment during the double-blind period prior to achieving the target reduction will be censored at the time of treatment discontinuation. Patients who never meet the target during the double-blind period will be censored at the time of analysis.

The following endpoints will be summarized descriptively for the double-blind period and compared between treatment groups using a CMH test controlling for the randomization stratification variables:

- the proportion of patients reaching a confirmed 40% reduction in eGFR, ESRD, or death. (ESRD is defined as initiation of RRT or sustained eGFR <15 mL/min/1.73 m² during the study);
- the proportion of patients requiring initiation of or intensification in immunosuppressive medication during the study;
- the proportion of patients with reduction in immunosuppressive medication during the study.

Changes from baseline to all post-baseline visits during the double-blind period with respect to QoL scores and blood pressure (systolic and diastolic) values will be analyzed using a MMRM model analogous to the one described for changes from baseline in eGFR.

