6.5.5. Kidney Disease Quality of Life (KDQOL) Survey

KDQOL-36 is a short form questionnaire that includes the Short Form Health Survey (SF-12) as generic core plus the burden of kidney disease, symptoms/problems with kidney disease, and effects of kidney disease scales from the KDQOL-SF v1.3. Below are the included items:

- Items 1-12: SF-12 v2
- Items 13-16: Burden of kidney disease (4 items)
- Items 17-28b: Symptoms/problems of kidney disease (12 items)
- Items 29-36: Effects of kidney disease (8 items)

Each question in KDQOL-36 is pre-coded with a numeric value, and out-of-range responses will be recorded as missing. Missing values will not be imputed. Survey responses will be scored based on adaptations from the KDQOL-SF v1.3 scoring manual (Hays 1997) and SF-12 scoring guide (Maruish 2012), as outlined below:

1. For items 13 to 36, raw pre-coded numeric values will be transformed to 0 to 100 possible range, with the higher transformed scores always reflecting better quality of life. Scores present the percentage of total possible scores achieved. Transformations per items are specified in Table 3 below.

Table 3: Transformations of Pre-coded Values for KDQOL-36

Applicable Items	Pre-coded Value	Transformed Score (0-100)
Items 13-16	1	0
	2	25
	3	50
	4	75
	5	100
Items 17-27, 28a, 28b, 29-36	1	100
	2	75
	3	50
	4	25
	5	0

KDQOL = Kidney Disease Quality of Life.

2. The following 3 subscales will be computed as the average of available items (transformed scores) within each subscale:

Table 4: KDAQOL Subscales

Sub-scale	Average of Available Items (Transformed Scores)
Symptoms/Problems List	Items 17-28 (12 items)
Effects of Kidney Disease	Items 29-36 (8 items)
Burden of Kidney Disease	Items 13-16 (4 items)

KDAQOL = Kidney Disease Quality of Life.

3. For items 1 to 12, scale scores and physical (PCS) and mental component summary (MCS) measures will be computed using a norm-based method in the following steps:
 - Recode 4 items that require recoding; a higher score indicates better functioning:

Table 5: SF-12 v2 Items Recoding

Items	Response Choices	Pre-coded Item Value	Final Item Value
1 – General health	Excellent	1	5.0
	Very good	2	4.4
	Good	3	3.4
	Fair	4	2.0
	Poor	5	1.0
5 – How much did pain interfere with your normal work	Not at all	1	5
	A little bit	2	4
	Moderately	3	3
	Quite a bit	4	2
	Extremely	5	1
6a – Felt calm and peaceful 6b – Energy	All of the time	1	5
	Most of the time	2	4
	Some of the time	3	3
	A little of the time	4	2

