8.7. Analysis of the Secondary Efficacy Endpoints

8.7.1. Percent Change of eGFR from Week 6 to Week 108

The percent change of eGFR from Week 6 to Week 108 will be analyzed at the final analysis based on the FAS, using MMRM. The dependent variable will be all available on-treatment natural log(eGFR) data from Week 2 to Week 108. The model will include the following fixed effects:

- Treatment group (2 levels: sparsentan, irbesartan)
- Baseline eGFR in log scale
- Visit (categorical)
- Treatment group by visit interaction
- Randomization stratification variable (4 levels based on Screening eGFR and total urine protein)

In addition, patient will be included as a random effect.

The model will utilize restricted maximum likelihood estimation with Kenward-Roger method used to compute the denominator degrees of freedom for tests of fixed effects. An unstructured covariance matrix will be assumed. If convergence issues arise, autoregressive-1 covariance structure will be used.

Statistical significance of the treatment effect at Week 108 will be assessed by comparing with the treatment effect at Week 6. The LS mean estimate from the MMRM model will be used to perform treatment group comparisons. Estimates and CIs will be converted to percentages via the following transformations:

$$[\exp(\text{least squares mean change from Week 6 in natural log(eGFR)}) - 1] \times 100$$

Robustness of the analysis due to missing data and premature treatment discontinuations will be explored by the following sensitivity analyses:

- MMRM using multiple imputation
- MMRM using treatment completers only (patients who completed blinded treatment)

To assess the impact of changes in immunosuppressive medications, the analysis will be repeated by excluding assessments after initiation or intensification of immunosuppressive medication in the blinded treatment period.

To assess the potential impact of patient evaluability and major protocol deviations, the analysis will be repeated using the PP Analysis Set.

8.7.2. Change in eGFR from Baseline to 4 Weeks Post-cessation of Randomized Treatment (Week 112)

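### SAP 8.8.5 refers the exploratory quality-of-life and blood-pressure analyses to the log-scale percent-change model (8.8.1.4), in conflict with the protocol; 8.8.1.3 was probably meant

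*SAP*

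**What the plan says.** SAP 8.8.5 covers the KDQOL, PedsQL, EQ-5D-5L index and VAS, EQ-5D-Y VAS, and systolic and diastolic blood pressure. It speaks of changes from baseline and assigns them an "MMRM model analogous to the one described in Section 8.8.1.4 for eGFR percent change from baseline". Blood pressure is also analysed this way at the interim analysis, through Week 60.

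SAP 8.8.1.4 opens: "For the analysis of eGFR percent change from baseline by visit, an MMRM approach analogous to the model described in" Section 8.7.1. It then back-transforms the estimates with the exponential formula for percent change. In SAP 8.7.1 the scale is explicit: "The dependent variable will be all available on-treatment natural log(eGFR) data from Week 2 to Week 108". The baseline covariate there is logged too.

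The subsection just before, SAP 8.8.1.3, gives the same MMRM for absolute change, "except that the response variable and corresponding baseline value is in original scale rather than natural log scale". SAP 8.8.5 does not cite it.

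Protocol 12.7.3, with matching text in the synopsis, analyses quality of life and blood pressure using a "model analogous to the one described for changes from baseline in eGFR". In the same section, log UP/C is given a model "analogous to the one described for percent change from baseline in eGFR".

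SAP 5.4 declares the SAP consistent with Protocol Amendment 6 apart from one exception, which concerns the analysis set for the surrogate endpoint.

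**The concern.** Two things do not fit. The SAP and the protocol appear to prescribe different scales for the same endpoints, and the difference is not declared. Also, the log model does not suit the data it is assigned to. Several of the quality-of-life scores can be exactly zero, and zero has no logarithm. SAP 8.1 justifies the log scale for UP/C by its skewness; no reason is given for using it on quality of life or blood pressure.

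At stake is how these exploratory results are computed and read. A literal fit could not use the worst attainable scores, would give small changes at the low end of a scale far more weight than equal point changes at the high end, and would express the blood-pressure treatment contrast as a ratio. Two programmers working from this text could also choose different scales.

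**Working it through.** The plan states no figure for this point, so there is none to reproduce. The check has three parts.

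**1. Which model each document points to**

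- SAP: 8.8.5 → 8.8.1.4 → 8.7.1. This ends at a log response with a log baseline. Section 8.8.5 names the percent-change model in words as well as by number.
- Protocol 12.7.3 describes two by-visit eGFR models. One is for absolute change: "For the analysis of eGFR absolute change from baseline by visit, a MMRM model will be fitted to the available eGFR data". The other is for percent change and uses logged values. UP/C is sent to the percent-change model by name. Quality of life and blood pressure are sent to the model for changes, without the word percent. The contrast points to the original-scale model, which is SAP 8.8.1.3.
- Versions: the SAP cites Amendment 6 and the protocol reviewed is Amendment 9. The protocol history for Amendments 7 to 9 lists no change to this analysis, though it does mention minor consistency edits.

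**2. Where the logarithm is undefined**

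Inputs are the scoring rules in SAP 6.5.5 (Tables 3, 4, 7 and 8), 6.5.6, 6.5.7 and 6.5.8.

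- KDQOL kidney subscales: for items 13 to 36, "raw pre-coded numeric values will be transformed to 0 to 100 possible range", and each subscale is the average of its items. All four burden items pre-coded 1 give (0+0+0+0)/4 = 0. All symptom or all effect items pre-coded 5 also give 0.
- PedsQL: every item answered 4 gives 0.
- EQ VAS (adult and youth): 0 is the bottom of the scale.
- SF-12 scales: norm-based score = 50 + 10 × (score − mean)/SD. The lowest attainable value is for Role Emotional: 50 + 10 × (0 − 86.41051)/22.35543 = 11.3. All eight scales stay positive.
- Physical summary: theoretical minimum 4.3, so positive.
- Mental summary: the minimum occurs with the four negatively weighted scales at 100 and the four positively weighted scales at 0. Coefficient × z-score gives PF −0.149, RP −0.088, BP −0.072, GH −0.019, VT −0.527, SF −0.909, RE −1.678, MH −1.663. The sum is about −5.105, and 50 + 10 × (−5.105) ≈ −1.0. With all eight scales at their worst the score is 16.0, so a non-positive value needs that particular mixed pattern.
- EQ-5D-5L index: the SAP does not give its range, so it is left out.

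Because the baseline is also logged, a zero at baseline would leave that patient's covariate undefined at every visit for that scale. The SAP gives no offset or other rule for zero or negative scores.

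**3. What the log scale does to defined values**

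On the burden subscale, one step on one item is 25/4 = 6.25 points.

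- From 6.25 to 12.5: +100%, ln(12.5/6.25) = 0.693.
- From 87.5 to 93.75: +7.1%, ln(93.75/87.5) = 0.069.

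The same one-step change therefore counts about ten times as much at the low end (0.693/0.069 ≈ 10).

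For blood pressure no value is lost, but a 10 mmHg fall becomes:

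- −10/110 = −9.1%
- −10/130 = −7.7%
- −10/160 = −6.3%

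**The case against.** The best counter-argument is that nobody intended a log analysis here. Section 8.8.5 speaks of changes from baseline, calls the model only analogous, and contains no exponential back-transformation, whereas SAP 8.7.1, 8.8.1.4, 8.8.1.5, 8.8.2.2 and 8.8.3 each print one. SAP 6.5.3 defines change from baseline as a simple difference and log-scale percent change separately. The sentence in 8.8.5 ends with a stray repeated verb, which suggests pasted text. The declaration of consistency in SAP 5.4 also favours the original scale.

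Most of this stands, and it makes a misdirected cross-reference the likeliest explanation. It does not settle the matter. SAP 8.8.3 also says change from baseline while using the log model, so that phrase alone does not fix the scale, and 8.8.5 names the percent-change model in words. As written, the instruction still leads to the wrong model.

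Four stronger readings are tempting, and the documents do not support them:

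- A reader might infer that the SAP drops zero scores. It says nothing of the kind. Loss would follow only from literal programming, and an undefined logarithm might well expose the error at that stage.
- A reader might infer that all KDQOL output runs from 0 to 100. The SF-12 scales and summaries are analysed as norm-based scores, and only the mental summary can fall to zero or below.
- A reader might infer that mmHg results would disappear. SAP 10.5 separately summarises blood pressure and its change from baseline at each visit, with mmHg thresholds. Only the modelled contrast would change scale.
- A reader might say that the protocol expressly requires absolute change for these endpoints. It does not use that word for them; the reading is a strong inference from the contrast with UP/C.

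**Conclusion.** The point holds as a conflict between SAP 8.8.5 and Protocol 12.7.3 that SAP 5.4 does not declare. It is an error in an analysis instruction, probably a wrong section number. If followed literally, it gives a model that cannot handle attainable scores on the three kidney subscales, the PedsQL scales and the VAS, and in one extreme pattern the mental summary. It would also turn the modelled blood-pressure effect into a ratio.

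Its reach is limited. These endpoints are exploratory (SAP 3.2.3) and outside the testing hierarchy (SAP 8.4), so alpha, sample size and every primary, surrogate and secondary conclusion are untouched. How many records would be affected cannot be estimated, because neither document gives the share of zero scores. The conclusion assumes that the protocol's plain wording means the original-scale model and that Amendments 7 to 9 left this text unchanged in substance.

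**What to change.** In SAP 8.8.5, replace the reference to Section 8.8.1.4 with Section 8.8.1.3, change the accompanying words from percent change to absolute change, and state that quality of life and blood pressure are analysed on the original scale. Every score, including zero and negative values, can then be analysed, and the SAP agrees with the protocol.

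If the log scale was in fact intended, list it in SAP 5.4 as a departure, give the reason, and add a rule for zero and negative scores.

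The cost is one cross-reference and one sentence. Data collection, sample size and alpha do not change.
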